#### **9.7.1.1 Study Endpoints**

##### **9.7.1.1.1 Primary Endpoints**

- Change at the 18th week from baseline in daily “off” time

- Change at the 18th week from baselines in PDQ-39 score

#### 9.7.1.1.2 Secondary Endpoints

- Change at the 18th week from baseline in below assessments:
  - Movement Disorder Society-Unified Parkinson's Disease Rating (MDS-UPDRS) Part 3
  - Movement Disorder Society-Unified Parkinson's Disease Rating (MDS-UPDRS) Part 4
  - King's Parkinson's disease Pain Scale (KPPS)
  - Mini-Mental State Examination (MMSE)
- Safety of safinamide mesilate
- Change at the 18th week from baseline in daily "on" time without dyskinesia

#### 9.7.1.2 Definitions of Analysis Sets

The Safety Analysis Set (SAS) is the group of subjects who received at least 1 dose of study drug and completed at least 1 post-dose safety assessment. The Full Analysis Set (FAS) is the group of subjects who received at least 1 dose of study drug and had at least 1 post-dose daily "off" time or PDQ-39. The Per Protocol Set (PPS) is for subjects who have fully complied with the study protocol. The details of the evaluability criteria will be determined prior to database lock and will be specified in the statistical analysis plan.

#### 9.7.1.3 Subject Disposition

The disposition of subjects will be tabulated as follows:

- Number of screened subjects
- Number of screening failed subjects and reasons for screening failure
- Number of discontinued subjects and reasons for discontinuation
- Number of subjects who completed the study

The analysis set of subjects will be tabulated as follows:

- Number of subjects for the SAS
- Number of subjects who were excluded from the SAS and reasons
- Number of subjects for the FAS
- Number of subjects who were excluded from the FAS and reasons

- Number of subjects for the PPS
- Number of subjects who were excluded from the PPS and reasons

#### **9.7.1.4 Demography**

Demography for the SAS and FAS will be summarized using descriptive statistics. Continuous demographic and baseline variables include age, height, weight; categorical variables include sex, age group.

#### **9.7.1.5 Medical History**

All investigator terms for medical history recorded in the CRF will be coded by System Organ Class (SOC) and Preferred Term (PT) using the Medical Dictionary for Regulatory Activities (MedDRA).

The number (percentage) of subjects who have medical history will be summarized using descriptive statistics on the SAS. The medical history will be classified by SOC and PT.

Surgical history will be performed on the SAS. The number (percentage) of subjects with surgical history will be summarized. The history of surgical operation will be classified according to SOC and PT.

#### **9.7.1.6 Prior and Concomitant Medications**

All investigator terms for medications recorded in the CRF will be coded to the Anatomical Therapeutic Chemical (ATC) code. The number (percentage) of subjects who took prior and concomitant medications will be summarized on the SAS by ATC class. If the SAS and FAS differ substantially, then the prior and concomitant medications summaries will be repeated on the FAS.

Prior medications will be defined as medications that stopped before the first dose of study drug.

Concomitant medications will be defined as medications that (1) started before the first dose of study drug and are continuing at the time of the first dose of study drug, or (2) started on or after the date of the first dose of study drug up to Visit 4 (EOT) Visit. All medications will be presented in subject data listings.

#### **9.7.1.7 Efficacy Analyses**

All efficacy analysis will use FAS as the primary population and PPS as the secondary population. Efficacy data will be summarized using descriptive statistics (e.g., n, mean, standard deviation, median, minimum, maximum for continuous variables; n [%] for categorical variables). Each variable and the difference from baseline will be used for summary statistics.

#### **9.7.1.7.1 Primary Efficacy Analyses**

Two primary efficacy parameters, which are daily “off” time and PDQ-39, will be analyzed.

The daily “off” time will be analyzed using a paired t-test on the change at the 18th week from baseline. The descriptive statistics for the daily “off” time will be summarized by each visit.

The PDQ-39 will be analyzed using a paired t-test on the change at the 18th week from baseline. The descriptive statistics for the PDQ-39 will be summarized by each visit.

#### **9.7.1.7.2 Secondary Efficacy Analyses**

For the following items, the descriptive statistics will be summarized by each visit, and it will be analyzed using a paired t-test on the change at the 18th week from baseline.

- MDS-UPDRS Part 3
- MDS-UPDRS Part 4
- KPPS
- MMSE
- Daily “on” time without dyskinesia

#### **9.7.1.8 SAFETY ANALYSES**

All safety analyses will be performed on the SAS. Safety data will be summarized using descriptive statistics (e.g., n, mean, standard deviation, median, minimum, maximum for continuous variables; n [%] for categorical variables). Safety variables include Treatment-Emergent Adverse Events (TEAEs), clinical laboratory parameters, and vital signs.

##### **9.7.1.8.1 Extent of Exposure**

Descriptive statistics for the extent of exposure during the study period will be summarized.

The extent of exposure to the study drug should be characterized according to the number of subjects exposed, the duration of exposure, and the dose to which they were exposed.

Compliance for the study drug will be calculated on the basis of the number of tablets dispensed, lost and returned. Summaries will provide descriptive summary statistics and number (percentage) of subjects below 80%, between 80% and 120%, and greater than 120%.

##### **9.7.1.8.2 Adverse Events**

The AE verbatim descriptions (investigator terms from the CRF) will be classified into standardized medical terminology using the Medical Dictionary for Regulatory Activities

(MedDRA). AEs will be coded to the MedDRA (Version 23.0 or higher) Lower Level Term (LLT) closest to the verbatim term. The linked MedDRA PT and primary SOC are also captured in the database.

A TEAE is defined as an AE that emerges during treatment, having been absent at pretreatment (Baseline) or

- Reemerges during treatment, having been present at pretreatment (Baseline) but stopped before treatment, or
- Worsens in severity during treatment relative to the pretreatment state, when the AE is continuous.

Only those AEs that are treatment-emergent will be included in summary tables. All AEs, treatment-emergent or otherwise, will be presented in subject data listings.

The incidence of TEAEs will be reported as the number (percentage) of subjects with TEAEs by SOC and PT. A subject will be counted only once within SOC and PT, even if the subject experienced more than 1 TEAE within a specific SOC and PT. The number (percentage) of subjects with TEAEs will also be summarized by maximum severity (mild, moderate, or severe).

The number (percentage) of subjects with TEAEs will also be summarized by relationship to study drug (Yes [related] and No [not related]).

The number (percentage) of subjects with treatment-related TEAEs will be summarized by SOC and PT. Treatment-related TEAEs include those events considered by the investigators to be related to the study drug. The number (percentage) of subjects with treatment-related TEAEs will also be summarized by maximum severity (mild, moderate, or severe).

AEs will be summarized using the SAS. The number of AEs and number and incidence (%) of subjects with AEs will be summarized by dose level and overall. To obtain the incidence (%), the number of subjects with at least 1 event and the percentage of subjects with AEs by SOC and PT will be calculated. Incidence (%) by causal relationship with study drug and by severity will also be calculated. For clinically significant events, time of onset, and recovery will be reported.

The number (percentage) of subjects with TEAEs leading to death will be summarized by MedDRA SOC and PT. A subject data listing of all AEs leading to death will be provided.

The number (percentage) of subjects with treatment-emergent Serious Adverse Events (SAEs) will be summarized by MedDRA SOC and PT. A subject data listing of all SAEs will be provided.

The number (percentage) of subjects with TEAEs leading to discontinuation from the study drug will be summarized by MedDRA SOC and PT. A subject data listing of all AEs leading to discontinuation from the study drug will be provided.

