### 7.2 Clinical Experience

Clinical trials with safinamide mesilate, which were 24-week, phase III, double-blind, parallel-group, randomized, multi-center, and multinational trials, demonstrated efficacy and safety in Parkinson's Disease patients with mid-to-late stage experiencing motor fluctuations (NCT01187966 and NCT 00627640). According to approved Food and Drug Administration (FDA) label, most common adverse reactions associated with safinamide mesilate treatment in which the incidence for Safinamide mesilate 100 mg/day was at least 2% greater than the incidence for placebo were dyskinesia, fall, nausea, and insomnia (Table 1).

**Table 1. Incidence of patients with adverse reaction in the safinamide mesilate 50mg/day and 100 mg/day groups compared to placebo in clinical trials**

	Safinamide mesilate 50 mg/day (N=223)	Safinamide mesilate 100 mg/day (N=498)	Placebo (N=497)
Adverse reaction	(%)	(%)	(%)
Dyskinesia	21	17	9
Fall	4	6	4
Nausea	3	6	4

	Safinamide mesilate 50 mg/day (N=223)	Safinamide mesilate 100 mg/day (N=498)	Placebo (N=497)
Adverse reaction	(%)	(%)	(%)
Insomnia	1	4	2
Orthostatic hypotension	2	2	1
Anxiety	2	2	1
Cough	2	2	1
Dyspepsia	0	2	1

In addition, phase II/III clinical trials in Japan indicated the efficacy and safety of safinamide mesilate as add-on therapy to levodopa in Parkinson's Disease patients. In this clinical trial, the most common AEs were nasopharyngitis, dyskinesia, and fall. Among these, the most common adverse drug reaction were dyskinesia and visual hallucinations (Table 2).

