**Table 2. Incidence of patients with AEs and adverse drug reaction**

	Adverse events			Adverse drug reaction		
	Placebo (N=141)	Safinamide mesilate		Placebo (N=141)	Safinamide mesilate	
		50 mg/day (N=133)	100 mg/day (N=132)		50 mg/day (N=133)	100 mg/day (N=132)
Nasopharyngitis	11.3	6.8	12.9	-	-	-
Dyskinesia	2.1	8.3	10.6	2.1	8.3	10.6
Fall	5.0	5.3	6.8	2.1	1.5	0.8
Contusion	2.8	3.0	5.3	-	-	-
Visual hallucinations	1.4	3.0	4.5	1.4	3.0	4.5
Back pain	3.5	0.8	3.8	-	-	-
Nausea	0.7	3.0	3.0	0.7	2.3	2.3
Conjunctivitis	0.7	-	3.0	-	-	-
Excoriation	-	-	3.0	-	-	-
Headache	0.7	3.8	1.5	-	2.3	1.5

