### 9.1.3 Treatment Period

Subjects whose screening assessments including the wash-out period and evaluations are completed and reviewed by the investigators and who continue to meet all of the inclusion/exclusion criteria will enter the Treatment Period. Subjects will take the study drug every day for 18 weeks.

The dose of the study drug is 50 mg once a day for 2 weeks (14 days) starting from the next day after Visit 2 (Baseline), and 100 mg once a day afterwards. Subjects who need to increase the dose at the discretion of an investigator shall visit the site (unscheduled) prior to the dose increase.

Subjects whose dose cannot be increased to 100 mg/day within 4 weeks following Visit 2 (Baseline) will be dropped out from the clinical trial.

If Adverse Events (AE) occur in subjects who have increased the dose, the dose may be reduced back to 50 mg/day at the discretion of an investigator through unscheduled site visit or phone visit. After reduction from 100mg/day to 50mg/day, the dose may be increased back to 100 mg/day at the discretion of an investigator.

Subjects will return to the site at 8 weeks and 18 weeks for Visit 3 and Visit 4 (EOT), respectively. The “windows” permitted for Visit 3 (8 weeks) will be -4 weeks and +2 weeks; for Visit 4 (18 weeks: EOT) will be +/- 2 weeks. Safety assessments including AE assessment, 12-lead ECG (if deemed necessary by an investigator), vital signs, weight, physical examination, clinical laboratory tests (hematology, chemistry, and urinalysis), and urine pregnancy test (females of childbearing potential only) will be conducted according to the schedule for each visit during Treatment Period. Efficacy assessments including PDQ-39, MDS-UPDRS Part 3 and Part 4, KPPS, and MMSE will be conducted at Visit 4 (EOT). Subjects will complete the diary for at least 3 consecutive days prior to Visit 4 (EOT), and the investigators will review the completed diary together with subjects at Visit 4 (EOT).

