## 9.4 Treatment

### 9.4.1 Treatment Administered

Subjects who are enrolled in this study will be treated with the study drug for approximately 18 weeks. The dose and administration of the study drug is as follow:

The dose of the study drug is 50 mg once a day for 2 weeks (14 days) starting from the next day after Visit 2 (Baseline), and 100 mg once a day afterwards. Subjects who need to increase the dose at the discretion of an investigator shall visit the site (unscheduled) prior to the dose increase.

If Adverse Events (AE) occur in subjects who have increased the dose, the dose may be reduced back to 50 mg/day at the discretion of an investigator through unscheduled site visit or phone visit. After reduction from 100mg/day to 50mg/day, the dose may be increased back to 100 mg/day at the discretion of an investigator.

If, following the dose increase to 100mg/day, moderate or severe hepatic impairment occurs according to Child-Pugh classification, study drug should be administered as per below guideline.

- Moderate hepatic impairment (Child-Pugh B): Do not exceed 50 mg once daily
- Severe hepatic impairment (Child-Pugh C): Contraindicated (Termination of study drug required)

[Child-Pugh Classification]

Parameter	Abnormal value or degree	Grade Score
Encephalopathy*	None 1 and 2 3 and 4	1 2 3
Ascites	None Mild Moderate	1 2 3
Total bilirubin (mg/dL)	< 2 2 - 3 > 3	1 2 3

Albumin (g/dL)	> 3.5	1
	2.8 - 3.5	2
	< 2.8	3
Prothrombin Time (seconds)	< 4	1
	4 - 6	2
	> 6	3

\*Grade 0: Normal values for cognition, behavior, neurological examination and ECG  
Grade 1: Anxiety, sleep disorder, easily irritated/excited, tremor, dysgraphia, 5 cps wave  
Grade 2: Narcolepsy, confusion of time, inappropriate behavior, asterixis, ataxia, decreased triphasic wave  
Grade 3: Narcosis, stupor, confusion of sense of space, excessive reflection, contracture, decreased brain wave  
Grade 4: Coma, lack of personality/action, decerebrate rigidity, slow delta wave of 2-3 cps

Total Score	Class	Seriousness
5 - 6	A	Mild
7 - 9	B	Moderate
10 -15	C	Severe

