#### **9.4.3 Method of Assigning Subjects to Treatment Group**

This is a multi-center, open-label, single-arm, interventional study. All subjects who provide signed informed consent to participate in this study and satisfy all eligibility requirements (see Section 9.3) will be assigned to receive the study drug daily for approximately 18 weeks as add-on therapy to levodopa. There is no randomization in this study.

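### Minor: crude AE percentages by dose level compare about 2 weeks with about 16 weeks of one titrated cohort, so neither their size nor their direction can be read as a dose effect

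*Combined protocol and SAP*

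**What the plan says.** Section 9.7.1.8.2 of the protocol plans a by-dose AE table: "The number of AEs and number and incidence (%) of subjects with AEs will be summarized by dose level and overall". It defines incidence through "the number of subjects with at least 1 event and the percentage of subjects with AEs by SOC and PT will be calculated". The AE summaries use the Safety Analysis Set (SAS).

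The design makes dose a period within a subject:

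- Section 9.4.3 describes a single arm and adds: "There is no randomization in this study".
- Section 9.4.1 sets 14 days at 50 mg once daily and 100 mg thereafter. It also says: "If Adverse Events (AE) occur in subjects who have increased the dose, the dose may be reduced back to 50 mg/day". Re-escalation is allowed.
- Section 9.1.3 sets a limit on escalation: "Subjects whose dose cannot be increased to 100 mg/day within 4 weeks following Visit 2 (Baseline) will be dropped out from the clinical trial". It allows the 18-week visit to fall 2 weeks early or late.

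The protocol text does not say how an AE is assigned to a dose level or which subjects form the denominator at each level. It plans no AE rate per unit of exposure. Section 9.7.1.8.1 summarizes number exposed, duration and dose, but separately from the AE table. Sections 9.7 and 9.7.1 leave further detail to a separate SAP, which is not in the material supplied.

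**The concern.** A percentage of subjects with at least one event grows with time at risk. On the nominal schedule each subject has about eight times as long at 100 mg as at 50 mg, so the 100 mg column collects events over a much longer period. The 50 mg column covers mainly the first two weeks on drug, when some AEs may cluster, plus any later time after an AE-driven reduction. Exposure, time since start and selection therefore all differ between the two columns.

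At stake is the reading of one descriptive table. The protocol's own background tables in section 7.2 (Table 1, "Incidence of patients with adverse reaction in the safinamide mesilate 50mg/day and 100 mg/day groups compared to placebo in clinical trials", and Table 2, "Incidence of patients with AEs and adverse drug reaction") give percentages for separate 50 mg and 100 mg groups. A by-dose column from this study would look the same without being comparable.

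**Working it through.** **Plan figures.** The protocol states no AE rate to reproduce. The only plan figures used are N = 199 and the 25% drop-out (section 9.7.2): 149/(1 - 0.25) = 198.7, rounded up to 199, which agrees.

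**Exposure ratio, 100 mg to 50 mg, before any dose reduction**

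- Nominal: 16/2 = 8.
- Escalation at week 4: 14/4 = 3.5; with the last visit at week 16, 12/4 = 3.
- Escalation at week 2 with the last visit at week 20: 18/2 = 9.

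**Assumptions for the crude percentages**

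- No dose effect.
- Each event counts at the dose taken at onset.
- The denominator is the subjects exposed at that level.
- Escalation is at week 2, with no later reduction.
- Drop-out is 25%, uniform over 18 weeks and unrelated to AEs.
- The 18-week incidence is p = 17%. This is borrowed from dyskinesia at 100 mg in Table 1; section 7.2 describes those trials as 24 weeks long.
- The hazard shape is not known, so several are shown.

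**Formulas.** Let H(t) be the cumulative hazard, with H(18) = -ln(1 - 0.17) = 0.1863, and let S(t) = 1 - 0.25t/18 be the proportion still in the study.

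- 50 mg: P = ∫ from 0 to 2 of (0.25/18)(1 - exp(-H(u))) du + S(2)(1 - exp(-H(2))).
- 100 mg: P = [∫ from 2 to 18 of (0.25/18)(1 - exp(-(H(u) - H(2)))) du + 0.75(1 - exp(-(H(18) - H(2))))] / S(2), with S(2) = 0.972.

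Hand check without drop-out, constant hazard: 0.1863/18 = 0.01035 per week; 1 - exp(-2 × 0.01035) = 2.05%; 1 - exp(-16 × 0.01035) = 15.26%; ratio 7.45.

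**Results with drop-out, p = 17%, no dose effect**

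| Hazard shape | 50 mg % | 100 mg % | % ratio 100:50 | Rate ratio 100:50 |
|---|---|---|---|---|
| Constant | 2.02 | 13.57 | 6.7 | 1.0 |
| 50% evenly in weeks 0-4 | 4.49 | 11.90 | 2.7 | 0.39 |
| 70% evenly in weeks 0-4 | 6.23 | 10.67 | 1.7 | 0.24 |
| 50% in weeks 0-2 | 8.77 | 7.89 | 0.90 | 0.13 |
| 70% in weeks 0-2 | 12.06 | 4.82 | 0.40 | 0.05 |

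The rate ratio compares events per person-time. For the fourth row it is (0.5/16)/(0.5/2) = 0.125. The choice of p matters less than the hazard shape: under a constant hazard the % ratio is 7.0 at p = 6% and 4.8 at p = 70%.

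**Size at N = 199**

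- Person-weeks per subject at 50 mg: 2 - 0.25 × 2²/36 = 1.972; × 199 = 392.
- Person-weeks per subject at 100 mg: 16 - 0.25 × (18² - 2²)/36 = 13.778; × 199 = 2,742.
- Subjects with an event, constant hazard: 199 × 0.0202 = 4 at 50 mg and 199 × 0.972 × 0.1357 = 26 at 100 mg.
- 50 mg rate: 4/392 = 1.0 per 100 person-weeks, exact 95% CI 0.28 to 2.6.

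**The assignment rule also matters.** Assume a hazard of 2% per week: 199 × (1 - exp(-0.36)) = about 60 subjects have an AE. If 20 of them end on 50 mg because of it, and nobody else does, assignment by last dose gives 20/20 = 100% at 50 mg and about 40/179 = 22% at 100 mg.

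**The case against.** The strongest reply is that this is a descriptive table with an overall column beside it. No objective or endpoint compares doses, exposure by duration and dose is summarized elsewhere, and the SAP may already define the rule and the denominator. All of this stands and keeps the point minor. A reader might infer that the SAP omits these rules; the documents cannot show that, because the SAP was not supplied. The mitigation is incomplete, though: a separate exposure summary does not alter a crude percentage.

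A second reply is that the remedy is partial. Stating the natural rule and denominator leaves the percentages as unequal as in the table above, and the rate can mislead in the opposite direction when events come early. That also stands. It is why the rate belongs beside the percentage and why the footnote is needed.

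Three stronger readings are tempting, and the documents do not support them:

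- *The crude percentage always favours 50 mg on the 14-day schedule.* It does not: with half or more of the hazard in weeks 0-2 the ratio falls below 1.
- *The artefact is larger than the dose differences in the background tables.* The 100:50 mg ratios there are 17/21 = 0.81 and 10.6/8.3 = 1.28 for dyskinesia, and 6/4 = 1.5 and 6.8/5.3 = 1.28 for fall. The no-effect ratio can lie above or below all of these.
- *AE onset dates may not be collected.* The promise to report time of onset for clinically significant events concerns reporting. The TEAE definition and the causality criteria already need onset timing for every AE.

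**Conclusion.** The point holds as a minor one. The planned by-dose percentages reflect exposure and time since start, so neither their size nor their direction can be read as a dose effect. With no dose effect, the 100:50 mg ratio runs from 6.7 down to 0.40 at 17% incidence, depending only on an assumed hazard shape. These ratios are illustrations that rest on the listed assumptions, not predictions.

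The unequal exposure follows from the protocol itself: 8:1 nominally, and about 3:1 to 9:1 across the escalation limit and the final-visit window. A reader might take 3.5:1 (escalation at week 4, 18 weeks of treatment) as the lower limit, but the visit window alone gives 3:1, and dose reductions can lower it further. The overall incidence, the main TEAE tables and the primary analysis are not affected.

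**What to change.** First check whether the separate SAP already covers this. If not, add to section 9.7.1.8.2 or the SAP:

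- Assign each TEAE to the dose being taken at its onset.
- At each dose level, use as denominator the SAS subjects who took at least one dose at that level.
- Beside n (%), show person-weeks at that level and TEAEs per 100 person-weeks.
- Footnote the table: dose levels are periods of one cohort that differ in exposure, time since start and AE-driven selection, and are not comparable groups.

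The cost is a short addition to the text, a footnote, two table columns and a little programming. Exposure by duration and dose is already to be summarized under section 9.7.1.8.1. There are two drawbacks: the 50 mg rate will be imprecise, and the rate corrects for unequal exposure only, not for time since start. This is a reporting change and touches no dosing rule.
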